 - c. Patients receiving off protocol lenalidomide maintenance cannot exceed 6 months post-transplant
 - d. A one week break from off protocol lenalidomide is suggested, prior to initiating treatment on the study
 - i. Any delays >7 days to align treatment with the start of Cycle 1 Day 1, of either arm, must be discussed with the PI.
 - e. Patients who completed tandem transplantation will be eligible for enrollment
- 2) No evidence of progressive disease on lenalidomide
- 3) Evidence of minimal residual disease at the time of screening defined as at least MRD-positive disease
 - a. A primary method of evaluation of MRD is Multi-parameter Flow Cytometry (MFC) performed at University of Chicago
 - b. Patients who have negative MRD by Multi-Parameter Flow Cytometry (MFC) but have residual original monoclonal protein by serum or urine immunofixation may be eligible if they are found to have MRD-positive disease by Next Generation Sequencing (NGS).
 - c. If patient is receiving lenalidomide, any delays required to align treatment with the start of Cycle 1 of either arm, must be discussed with the PI.
- 4) Bone marrow specimen will be required at study entry; available DNA sample will be used for calibration step for MRD evaluation by gene sequencing
- 5) Males and females ≥ 18 years of age
- 6) Life expectancy of more than 3 months
- 7) ECOG performance status of 0-2
- 8) Adequate hepatic function, with bilirubin $\leq 1.5 \times$ ULN and aspartate aminotransferase (AST) and alanine aminotransferase (ALT) $\leq 3 \times$ ULN
- 9) ANC $\geq 1.0 \times 10^9/L$, hemoglobin $\geq 8 \text{ g/dL}$, platelet count $\geq 75 \times 10^9/L$.
- 10) Calculated creatinine clearance (by Cockcroft-Gault) $\geq 50 \text{ ml/min}$ or serum creatinine below 2 g/dL (section 13.2)
- 11) Voluntary written consent must be given before performance of any study related procedure not part of standard medical care, with the understanding that consent may be withdrawn by the patient at any time without prejudice to future medical care.
- 12) Female patients who:
 - a. Are postmenopausal for at least 1 year before the screening visit, OR
 - b. Are surgically sterile, OR

- c. If they are of childbearing potential, agree to practice 2 effective methods of contraception, at the same time, from the time of signing the informed consent form through 90 days after the last dose of study drug, OR

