- 4) 12-lead ECG, including QTc interval completed on local machine.
- 5) For Day 1 of cycle 1, screening results may be used if within 7 days of treatment start.
- 6) Complete physical exam (including vital signs [systolic and diastolic blood pressure, respiration, pulse, and oral temperature], weight, calculation of body surface area [BSA] & ECOG score) required at screening & Day 1 of each cycle.
- 7) Systolic and diastolic blood pressure, pulse, respiration, temperature day 1 of each cycle, EOT visit and as clinically indicated.
- 8) Height required at screening only
- 9) 24 hour urine total protein, urine protein electrophoresis (UPEP), and urine protein immunofixation. For subjects whose disease is being monitored through UPEP, additional post baseline 24-hour urine collections are required as indicated
- 10) On day 1 of each cycle and EOT visit is required, and as clinically indicated at other time-points. Hemoglobin, WBC with complete differential, platelet count, absolute lymphocyte and absolute neutrophil counts. Results must be reviewed before dosing.
- 11) On day 1 of each cycle and EOT visit is required, and as clinically indicated at other time-points. Full serum chemistry panel at screening, day 1 of each cycle and at EOT visit: sodium, potassium, chloride, bicarbonate, BUN, creatinine, glucose, total protein, albumin, calcium, total bilirubin, alkaline phosphatase, ALT, AST, LDH, and CRP. Abbreviated serum chemistry panel should be included as necessary.
- 12) Pregnancy tests for females of childbearing potential. A female of childbearing potential (FCBP) is a sexually mature female who: 1) has not had a hysterectomy or bilateral oophorectomy; or 2) has not been naturally post-menopausal for at least 24 consecutive months (i.e., menses within the preceding 24 months) See Appendix F of protocol for details.

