4.2.1 Screening Procedures

The screening period is 42 days in length. Screening can only start after the patient has signed the Informed Consent Form.

Signed written informed consent	Obtained prior to performing any study specific assessments
Demographics and medical history	
• Age, gender, ethnic background• Details on myeloma diagnosis prior cancer therapy, including start and stop dates, transplant regimen, lenalidomide maintenance regimen• Previous and concurrent relevant diseases• Current symptoms and/ or residual toxicities
Pregnancy test (if applicable) (Day - 7 to -1)	A serum pregnancy test will be performed in pre-menopausal women and women who are post-menopausal for < 2 years. In case the sampling date for the serum pregnancy test exceeds 7 days before treatment start, a urine test is required for confirmation
Physical examination and vital signs	
• Body height and weight• BSA• ECOG Performance Status• Blood pressure, pulse, temperature• Physical examination

Cardiac evaluation	12-lead ECG required at screening (local machine)
Urinalysis	Urine bilirubin, glucose, hemoglobin, ketones, pH, protein.
Hematology (CBC)	Hemoglobin, hematocrit, mean corpuscular volume, mean corpuscular hemoglobin, mean corpuscular hemoglobin concentration, white blood cell (WBC) count, WBC differential, red blood cell count, lymphocytes, monocytes, neutrophils, band neutrophils, eosinophils, basophils, platelets. WBC differential may be automated or manual as per institutional standards. Reticulocytes may be done only when clinically indicated
Clinical chemistry	Sodium, potassium, chloride, bicarbonate, BUN, creatinine, glucose, calcium, phosphate, magnesium, ALT, AST, alkaline phosphatase, total bilirubin, total protein, albumin, uric acid, LDH, and CRP
CRP & β 2 microglobulin	Required at screening only
Myeloma Disease Assessment - laboratory	
M-protein determination:
 
• Serum Protein Electrophoresis (SPEP) and immunofixation• Urine Protein Electrophoresis (UPEP) and immunofixation• Serum Free Light Chains (SFLC)• Serum quantitative immunoglobulins (Igs) 
All of the above assessments are required at screening regardless of the disease classification.

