4.2.3 End of Treatment Procedures

Patients who discontinue therapy for any reason must have an end of treatment (EOT) visit completed 30 days (\pm 7 days) after the last application of study drug. Following the end of treatment, subjects will be followed for survival for 2 years.

Physical examination and vital signs	
• Body weight• Blood pressure, pulse, temperature• Physical examination• Pulse oximetry
Cardiac evaluation	12-lead ECG
Urinalysis	Urine bilirubin, glucose, hemoglobin, ketones, pH, protein
Hematology	Hemoglobin, hematocrit, mean corpuscular volume, mean corpuscular hemoglobin, mean corpuscular hemoglobin concentration, white blood cell (WBC) count, WBC differential, red blood cell count, lymphocytes, monocytes, neutrophils, band neutrophils, eosinophils, basophils, platelets. WBC differential may be automated or manual as per institutional standards. Reticulocytes may be done only when clinically indicated
Clinical chemistry	Sodium, potassium, chloride, bicarbonate, BUN, creatinine, glucose, calcium, phosphate, magnesium, ALT, AST, alkaline phosphatase, total bilirubin, total protein, albumin, uric acid, LDH, CRP

Pregnancy test (if applicable)	A serum pregnancy test will be performed in pre-menopausal women and women who are post-menopausal for < 2 years to exclude that a pregnancy occurred under treatment and in accordance with lenalidomide REMS™ (Appendix 13.6)
Myeloma Disease Assessment-laboratory	M-protein determination: 
• Serum Protein Electrophoresis (SPEP) and immunofixation• Urine Protein Electrophoresis (UPEP) and immunofixation• Serum Free Light Chains• Serum quantitative immunoglobulins (Igs)
Bone Marrow Biopsy	Quantify percent myeloma cell involvement, and obtain bone marrow aspirate for conventional cytogenetics and fluorescent in situ hybridization. A sample for MRD evaluation is required to be collected. For subjects who sign consent for correlative samples, an additional aspirate sample should be collected at screening (Section 8)
Correlative Samples	For patients who give consent, peripheral blood and bone marrow aspirate samples collected at End of Treatment
Neurotoxicity Assessment	Including Neurotoxicity Questionnaire (Appendix 5)
QOL Assessment	Patient reported survey
Adverse events	Record through 30-days after last treatment. All SAEs considered related to treatment must be followed until resolution.

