7.5 Precautions and Restrictions

- Fluid deficit should be corrected before initiation of treatment and during treatment.
- Nonsteroidal anti-inflammatory drugs (NSAIDs) should be avoided with impaired renal function given reported NSAID-induced renal failure in patients with decreased renal function.

Pregnancy

It is not known what effects ixazomib has on human pregnancy or development of the embryo or fetus. The use of lenalidomide in pregnant females and nursing mothers has not been studied nor has the effect of the lenalidomide on human eggs and sperm. Lenalidomide is structurally related to thalidomide. Thalidomide is a known human teratogenic active substance that causes severe life-threatening birth defects. An embryo/fetal development study in animals indicates that lenalidomide produced malformations in the offspring of female monkeys who received the drug during pregnancy. The teratogenic effect of lenalidomide in humans cannot be ruled out. Therefore, a risk minimization plan to prevent pregnancy must be observed.

Female patients participating in this study should avoid becoming pregnant, and male patients should avoid impregnating a female partner. Non-sterilized female patients of reproductive age group and male patients should use effective methods of contraception through defined periods during and after study treatment as specified below.

Female patients must meet 1 of the following:

- Postmenopausal for at least 1 year before the screening visit, or
- Surgically sterile, or

- If they are of childbearing potential, agree to practice 2 effective methods of contraception from the time of signing of the informed consent form through 90 days after the last dose of study drug, or
- Agree to practice true abstinence, when this is in line with the preferred and usual lifestyle of the subject. (Periodic abstinence [e.g., calendar, ovulation, symptothermal, post-ovulation methods] and withdrawal are not acceptable methods of contraception.)

Male patients, even if surgically sterilized (i.e., status post-vasectomy) must agree to 1 of the following:

- Practice effective barrier contraception during the entire study treatment period and through 90 days after the last dose of study drug, or

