- Agree to practice true abstinence, when this is in line with the preferred and usual lifestyle of the subject. (Periodic abstinence [e.g., calendar, ovulation, symptothermal, post-ovulation methods for the female partner] and withdrawal are not acceptable methods of contraception.)

All study participants must be registered into the mandatory lenalidomide REMS® program and be willing and able to comply with the requirements of lenalidomide REMS®. Before starting lenalidomide, FCBP must have 2 negative pregnancy tests (sensitivity of at least 50 mIU/mL) prior to initiating lenalidomide. The first pregnancy test must be performed within 10-14 days before, and the second pregnancy test must be performed within 24 hours before prescribing lenalidomide (prescriptions must be filled within 7 days). The subject may not receive lenalidomide until the investigator has verified that the results of these pregnancy tests are negative.

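### Women 12 to under 24 months after menopause are exempt from contraception under criterion 12 and Section 7.5, yet the Schedule of Events classes them as of childbearing potential

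*Combined protocol and SAP*

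**What the plan says.** Criterion 12 for female patients, in the Key Inclusion Criteria and again in Section 5.1, is a set of alternatives joined by OR. The first is "Are postmenopausal for at least 1 year before the screening visit, OR" and it carries no contraception duty. A separate alternative covers the other group: "If they are of childbearing potential, agree to practice 2 effective methods of contraception".

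The Pregnancy part of Section 7.5 repeats the set as a list of which one item must be met. Its first item is "Postmenopausal for at least 1 year before the screening visit, or". Just before that list the section states: "Therefore, a risk minimization plan to prevent pregnancy must be observed". Just after it comes: "All study participants must be registered into the mandatory lenalidomide REMS® program and be willing and able to comply".

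Footnote 12 of the Schedule of Events defines a female of childbearing potential. Its time condition is that she "has not been naturally post-menopausal for at least 24 consecutive months".

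The testing rules use the longer interval too. Section 4.2.1 requires a serum pregnancy test at screening in premenopausal women and in "women who are post-menopausal for < 2 years". Section 4.2.3 requires one at end of treatment in "women who are post-menopausal for < 2 years to exclude that a pregnancy occurred under treatment".

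**The concern.** Contraception in criterion 12 and Section 7.5 depends on childbearing potential, a term that only footnote 12 defines. By that definition a non-sterilised woman in her second year after menopause can still conceive. By the first alternative of criterion 12 she needs no contraception. The protocol thus treats the same woman as able to conceive when it tests her, but not when it decides whether pregnancy must be prevented.

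Both arms take lenalidomide, and the experimental arm also takes ixazomib. Section 7.5 describes lenalidomide as a structural relative of a known human teratogen, reports malformations in monkey offspring and leaves open a teratogenic effect in humans. Site staff who apply criterion 12 as printed would enrol these women without asking for contraception. The matter is participant safety and consistent eligibility, not inference.

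**Working it through.** No figure in the plan needs reproducing. The check sets the rules side by side and then measures how long the conflict lasts.

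**The rules**

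| Place | What it governs | Threshold |
|---|---|---|
| Criterion 12, Key Inclusion Criteria and Section 5.1 | Entry with no contraception duty | 1 year before screening |
| Section 7.5 list | Same, any one item is enough | 1 year before screening |
| Schedule of Events, footnote 12 | Definition of childbearing potential | 24 consecutive months |
| Section 4.2.1 | Pregnancy test at screening | under 2 years |
| Section 4.2.3 | Pregnancy test at end of treatment | under 2 years |

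**How a non-sterilised woman is classified**, if both thresholds are counted from the same starting point

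| Time since menopause at screening | Exempt under criterion 12? | Childbearing potential under footnote 12? |
|---|---|---|
| under 12 months | no | yes |
| 12 to under 24 months | **yes** | **yes** |
| 24 months or more | yes | no |

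Only the middle row conflicts. The gap is 24 − 12 = 12 months wide.

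**How long the conflict lasts on treatment**

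Inputs: 12 cycles of 28 days, and a screening window of day −42 to −1 (Schedule of Events). No dose delays are assumed.

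- Planned treatment: 12 × 28 = 336 days; 336 / 30.44 = 11.0 months.
- Woman exactly 12 months after menopause at a visit just before Cycle 1 Day 1: she reaches 12 + 11.0 = 23.0 months by the end of treatment, still under 24. Overlap: all 336 days (100%).
- Same woman screened 42 days before Cycle 1 Day 1: 365 − 42 = 323 days of the definition remain. Overlap: 323 / 336 = 96%.
- Woman nearing 24 months at entry: overlap tends to zero.
- Average across the gap, assuming that time since menopause at Cycle 1 Day 1 is uniform over 12 to 24 months: (336²/2 + 29 × 336) / 365 = (56,448 + 9,744) / 365 = 181 days, or 181 / 336 = 54%. Here 29 = 365 − 336.

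**Planned exposure over 12 cycles**

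- Control: lenalidomide on 28 × 12 = 336 days.
- Experimental: lenalidomide on 21 × 12 = 252 days, and 3 × 12 = 36 ixazomib doses.

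**The case against.** The strongest reply is that the lenalidomide REMS already governs. Section 7.5 makes registration and compliance mandatory for every participant, directly after the list, so criterion 12 is only an entry condition with REMS added on top. This may well close the gap in practice. It does not settle the text, because the REMS contraception rules are not reproduced. Appendix 14.6 holds only a link, and footnote 12 points to an Appendix F that is not among Appendices 14.1 to 14.7.

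A second reply is that footnote 12 belongs to the pregnancy-test row and criterion 12 does not cite it. Read alone, criterion 12 is coherent, and testing more women than must use contraception is not in itself a contradiction. But the contraception branch uses the same term and no other definition is given. If two meanings were intended, the protocol needed to say so.

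Third, these women are not unmonitored. Under footnotes 12 and 13 they are tested before prescribing, weekly for the first 28 days and regularly after that, and Section 7.5 withholds lenalidomide until the pre-treatment tests are verified negative. This stands as mitigation. After treatment starts, however, a test finds a pregnancy that has already been exposed; it does not prevent one.

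Fourth, 96% to 100% is the extreme case, the average is nearer half under the uniform assumption, and few women may be affected. That is fair, and it limits the size of the point without removing it.

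**Conclusion.** The inconsistency is real and should be corrected. As written, criterion 12 and Section 7.5 exempt from contraception a group whom footnote 12 classes as of childbearing potential. The 24-month figure is not an isolated slip, since Sections 4.2.1 and 4.2.3 use the same interval.

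Confidence is high for the mismatch in the text. The practical safety gap is less certain, because it depends on REMS rules that the documents do not show. The documents give no age or menopausal data, so the number of women affected is unknown; that it is small is an assumption. The durations assume 12 full cycles without delay. Nothing here changes the primary endpoint, the sample size, the type I error or the analysis.

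**What to change.** In criterion 12 (Key Inclusion Criteria and Section 5.1) and in the Section 7.5 list, replace the 1-year threshold with natural menopause of at least 24 consecutive months, to match footnote 12. A woman 12 to under 24 months after menopause who is not surgically sterile would then enter only by agreeing to two contraceptive methods or to abstinence. Do not resolve the conflict the other way by shortening the 2-year testing interval in Sections 4.2.1 and 4.2.3.

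As a clerical correction, point footnote 12 to Appendix 14.6, the REMS appendix, instead of Appendix F. Two related loose ends could be tidied in the same edit, although the fix does not depend on them: the word joining the two conditions in footnote 12, which read literally would class any woman without hysterectomy or bilateral oophorectomy as of childbearing potential, and how the surgically sterile branch relates to that footnote.

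The change is to wording only, but it alters an eligibility criterion and so needs an amendment with ethics approval under Section 12.6. The burden on participants is that women in the 12-month gap must agree to contraception or abstinence.

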14.6 Lenalidomide Risk Evaluation and Mitigation Strategy (REMS)™ Program	105
14.7 Lenalidomide Prescribing Information 2013	106

LIST OF ABBREVIATIONS AND GLOSSARY OF TERMS

Abbreviation	Term
5-HT ₃	5-hydroxytryptamine 3 serotonin receptor
AE	adverse event
ALL	acute lymphoblastic leukemia
ALP	alkaline phosphatase
ALT	alanine aminotransferase
AML	acute myelogenous leukemia
ANC	absolute neutrophil count
API	active pharmaceutical ingredient
aPTT	activated partial thromboplastin time
Ara-C	Cytarabine
ASCO	American Society of Clinical Oncology
AST	aspartate aminotransferase
AUC	area under the plasma concentration versus time curve
AUC _{24 hr}	area under the plasma concentration versus time curve from zero to 24 hours
AUC _{inf}	area under the plasma concentration versus time curve from zero to infinity
AUC _τ	area under the plasma concentration versus time curve from zero to next dose
BCRP	breast cancer resistance protein
βhCG	beta-human chorionic gonadotropin
BID	bis in die; twice a day
BM	bone marrow
BSA	body surface area
BUN	blood urea nitrogen
BZD	Benzodiazepines
CBC	complete blood count
CCTO	Cancer Clinical Trials Office (University of Chicago)
CFR	Code of Federal Regulations
CL	clearance, IV dosing
CL _P	plasma clearance
CL _{Total}	total clearance
C _{max}	single-dose maximum (peak) concentration
CNS	central nervous system
CO ₂	carbon dioxide
CR	complete response

Abbreviation	Term
CRM	continual reassessment method
CRP	C-reactive protein
CSF-1R	colony-stimulating factor 1 receptor
CT	computed tomography
C_{trough}	single-dose end of dosing interval (trough) concentration
CV	coefficient of variation
CYP	cytochrome P ₄₅₀
DDI	drug-drug interaction
DLT	dose-limiting toxicity
DME	drug metabolizing enzymes
DNA	deoxyribonucleic acid
ECG	Electrocardiogram
ECOG	Eastern Cooperative Oncology Group
eCRF	electronic case report form
EDC	electronic data capture
ELISA	enzyme-linked immunosorbent assay
EOS	End of Study (visit)
EOT	End of Treatment (visit)
EU	European Union
FDA	United States Food and Drug Administration
GCP	Good Clinical Practice
G-CSF	granulocyte colony stimulating factor
GGT	gamma glutamyl transferase
GI	Gastrointestinal
GLP	Good Laboratory Practices
GM-CSF	granulocyte macrophage-colony stimulating factor
GMP	Good Manufacturing Practice
Hb	Hemoglobin
Hct	Hematocrit
HDPE	high-density polyethylene
hERG	human ether-à-go-go related gene
HIV	human immunodeficiency virus
HNSTD	highest nonseverely toxic dose
IB	Investigator's Brochure
IC ₅₀	concentration producing 50% inhibition

Abbreviation	Term
ICF	informed consent form
ICH	International Conference on Harmonisation
IEC	independent ethics committee
IRB	institutional review board
ITT	intent-to-treat
IV	intravenous; intravenously
IVRS	interactive voice response system
K _i	inhibition constant
KPS	Karnofsky Performance Status
LDH	lactate dehydrogenase
LFT	liver function test(s)
MedDRA	Medical Dictionary for Regulatory Activities
Millennium	Millennium Pharmaceuticals, Inc., and its affiliates
MRI	magnetic resonance imaging
MRU	medical resource utilization
MTD	maximum tolerated dose
MUGA	multiple gated acquisition (scan)
NCCN	National Comprehensive Cancer Network
NCI	National Cancer Institute
NCI CTCAE	National Cancer Institute Common Terminology Criteria for Adverse Events
NPO	nothing by mouth
NYHA	New York Heart Association
PBMC	peripheral blood mononuclear cell
PCR	polymerase chain reaction
PD	progressive disease (disease progression)
Pgp	P-glycoprotein
PK	pharmacokinetic(s)
PO	per os ; by mouth (orally)
PR	partial response
PRO	patient-reported outcome
PSA	prostate-specific antigen
QD	quaque die ; each day; once daily
QID	quater in die ; 4 times a day
QOD	quaque altera die ; every other day
QOL	quality of life

Abbreviation	Term
QTc	rate-corrected QT interval (millisec) of electrocardiograph
RBC	red blood cell
RECIST	Response Evaluation Criteria in Solid Tumors
SAE	serious adverse event
SC	Subcutaneous
SD	stable disease
SmPC	Summary of Product Characteristics
$t_{1/2}$	terminal disposition half-life
TGI	tumor growth inhibition
T_{\max}	single-dose time to reach maximum (peak) concentration
UK	United Kingdom
ULN	upper limit of the normal range
US	United States
V_z	volume of distribution in the terminal phase
WBC	white blood cell
WHO	World Health Organization

